4.2 Exclusion Criteria

- prior mandibular surgery,
- primary intraosseous carcinoma,
- prior history of radiation to the mandible,
- obvious finding of clinical invasion of the mandible

4.3 Gender/Minority/Pediatric Inclusion for Research

All ethnicities will be included in this study of both male and female gender. The patients will be adults, 18 years of age or older and have a biopsy proven squamous cell carcinoma of the oral cavity.

While men have an increased incidence of oral SCC by 2:1 as compared to women, there will be no preference for one gender or another. Also, the ratio of men: women in the study will be monitored and all patients that meet the inclusion criteria will be added regardless of gender

4.4 Subject Recruitment and Screening

All patients will be from the Dept of OMS or JHNS practice. The patients will have a Cone Beam CT which will be used in the detection of mandibular or maxillary invasion by the oral squamous cell carcinoma as well as the evaluation of the dentition prior to possible radiation therapy.

4.5 Early Withdrawal of Subjects

4.5.1 When and How to Withdraw Subjects

Early withdrawal from the study is not foreseen as this study does not use any therapies of treatment, only radiologic tools for diagnosis

4.5.2 Data Collection and Follow-up for Withdrawn Subjects

Not applicable

5.0 STUDY DRUG/THERAPY

N/A

5.1 Description

Cone beam CT scan

5.2 Treatment Regimen

This study will compare helical, medical grade CT, PET/CT and CBCT for the ability to predict invasion of the maxilla or mandible. Currently, helical CT and PET/CT are routinely used. Currently, panoramic radiographs are taken for patients with oral SCC necessitating therapeutic radiation. These radiographs on average emit 24 Micro Sieverts of absorbed radiation to the patient. The CBCT which provides three dimensional imaging of the teeth and jaws yield approximately 85 Micro Sieverts, which is only a small increase of 60 Micro Sieverts, with the benefit being the ability to more accurately predict invasion or absence of extension of the carcinoma with the hope of more accurate surgical margins and the sparing of uninvolved tissue when invasion is absent.

5.3 Risks

Formerly, patients received a panoramic radiograph in the OMFS Department for evaluation of dentition prior to radiation. The experimental procedure will now include CBCT in place of a panoramic x-ray which will more accurately predict invasion of the maxilla or mandible, and give better resolution concerning the risk of osteoradionecrosis of the jaw, should radiation therapy be used in the future. Although CBCT has slightly more radiation as compared to

the panoramic radiograph (87 Micro Sieverts vs 24 Micro Sieverts), it has the ability to yield more information relevant to patient diagnostic benefit and as such these benefits outweigh the approximate 60 Micro Sievert increase in absorbed radiation dose.

Risk will be minimized by using the smallest field of view necessary to provide diagnostic benefit of the CBCT. In addition, patients will be adequately shielded using a lead apron and thyroid collar.

The relative increase in absorbed radiation dose between the panoramic radiograph and the CBCT is small in comparison to the potential improvement in quality of life for these patients if they can avoid locoregional recurrence, tracheotomy, feeding tubes, cosmetic deformity and loss of masticatory function and speech function. In addition, the increase of approximately 40 micro sieverts from the panoramic radiograph to the CBCT gives the image greater resolution and contrast as well as 3-dimensional representation of the image, greatly increasing the accuracy of the image.

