5.4 Method for Assigning Subjects to Treatment Groups

This study will not be randomized. All patients will received a helical CT, PET/CT and CBCT

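### Does the dose increase of about 40 microSv in section 5.3, given as about 60 elsewhere, undermine the protocol's risk statement?

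*Combined protocol and SAP*

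**What the plan says.** Section 5.2 gives a panoramic radiograph an average of 24 microSv and says that CBCT images "yield approximately 85 Micro Sieverts, which is only a small increase of 60 Micro Sieverts". Section 5.3 repeats the comparison with a slightly different CBCT dose, "the panoramic radiograph (87 Micro Sieverts vs 24 Micro Sieverts", and concludes that "these benefits outweigh the approximate 60 Micro Sievert increase in absorbed radiation dose". The last sentence of 5.3 then speaks of "the increase of approximately 40 micro sieverts from the panoramic radiograph to the CBCT", in the course of describing better resolution, contrast and three-dimensional display.

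Four other statements bear on how the increment is read.

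- **Who has the film.** Section 5.2 says that "panoramic radiographs are taken for patients with oral SCC necessitating therapeutic radiation". Section 4.4 describes CBCT as serving, among other things, "the evaluation of the dentition prior to possible radiation therapy".
- **Who has CBCT.** Section 5.4: "All patients will received a helical CT, PET/CT and CBCT".
- **Status of CBCT.** Section 5.3: "The experimental procedure will now include CBCT in place of a panoramic x-ray". Section 3.4, by contrast, states that the study carries no safety risk because the modalities are already standard of care.
- **Use of the result.** Section 6.1 keeps surgical planning blind to the CBCT. Section 8.3 provides for release to the surgeon if imaging is found to predict invasion accurately.

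**The concern.** The extra radiation is the only participant risk that the protocol puts a number on, and one section gives two numbers for it. The lower one cannot be derived from any stated doses, and it is the more favourable to the study. A reader who took 40 at face value would understate the increment by about a third.

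Three further points add to the unease. The increment subtracts a panoramic film that some participants might never have had. The stated surgical benefits may not reach participants whose surgeon is blinded to the CBCT. And 3.4 denies a risk that 5.3 goes on to quantify. If an ethics board's judgement of benefit against risk had rested on the wrong figure, the approval itself would be in question.

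**Working it through.** **Inputs.** Panoramic film: 24 microSv (5.2 and 5.3). CBCT: about 85 (5.2) or 87 (5.3). Stated increments: 60 (5.2), about 60 (5.3), about 40 (5.3, last sentence).

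**Step 1: reproduce the stated 60.** Increment = CBCT dose − panoramic dose.

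- Section 5.2 doses: 85 − 24 = 61.
- Section 5.3 doses: 87 − 24 = 63.

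Both round to 60 at the nearest ten, so the approximate 60 reproduces in both sections.

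**Step 2: try to reproduce 40.** With the film at 24, an increment of 40 needs a CBCT dose of 24 + 40 = 64. With CBCT at 85 or 87, it needs a film dose of 85 − 40 = 45 or 87 − 40 = 47. None of these doses appears in the document. The shortfall is 61 − 40 = 21 (21/61 = 34%) or 63 − 40 = 23 (23/63 = 37%), which is too large for rounding.

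**Step 3: the 85 and 87.** They differ by 2 microSv. Section 5.2 marks its value as approximate, and both lead to the same rounded increment.

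**Step 4: what rests on each figure.**

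| Figure | Where | Role |
|---|---|---|
| 60 | 5.2 | describes the increase as small and sets it beside the hoped-for benefit |
| about 60 | 5.3, first paragraph | the sentence that weighs benefit against dose |
| about 40 | 5.3, last sentence | a remark on image quality |

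No figure goes further. Eligibility (4.1, 4.2) has no dose criterion. Sample size (7.1) comes from yearly case numbers. The analysis (7.2) uses counts of true and false positives and negatives against histology. The stopping rule (8.4) names no dose.

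**Step 5: the comparator.** For a participant who would not otherwise have had a film, the added dose is the full 85 or 87. That exceeds the net increment by 85 − 61 = 24 or 87 − 63 = 24, which is simply the film's own dose. The protocol does not say how many participants this covers. Section 5.2 read alone limits the film to patients who need radiation. Section 4.4, and the mention in 5.3 of radiation that might be used later, fit a dental work-up done whenever radiation is a possibility. On that reading, few or no participants lack a displaced film.

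**Step 6: the benefit.** Sections 5.2 and 5.3 express the surgical gains as a hope, as potential, and as conditional on avoiding bad outcomes. They do not promise them to each participant. Section 6.1 blinds surgical planning. I infer that the dental and osteoradionecrosis assessment lies outside that blind. Section 8.3 gives the surgeon a route to the information, though without a threshold or a date.

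**The case for a change.** The strongest case for a change is that risk text should be exact because a board relies on it. The figure that cannot be derived is also the flattering one, and correcting it costs only a few words. The conflict between 3.4 and 5.3 points the same way: section 5.2 names only helical CT and PET/CT as routine, so resting the denial of risk on standard of care does not plainly cover CBCT.

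Much of this stands. The two increments contradict each other, 3.4 and 5.3 do not agree, and the passages must be reconciled to one CBCT dose and its difference from the film dose. I do not say which dose is right.

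What does not stand is the inference that the benefit-risk judgement was misled. The sentence that makes the judgement uses the figure that reproduces, and the same section prints both doses, so any reader can do the subtraction. The comparator argument depends on taking 5.2 without 4.4 and the rest of 5.3. The benefit argument passes over the conditional wording. The absence of an unblinding threshold in 8.3 is a separate design question and does not turn on the dose.

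**Conclusion.** The slip is genuine but clerical. One sentence understates the increment by 21 to 23 microSv relative to the protocol's own doses, while both statements that set benefit beside dose use about 60, against a computed 61 or 63. Removing the discrepancy would alter no procedure, no analysis and no conclusion that the study can reach. The mismatch between 3.4 and 5.3 is of the same kind, and the questions about who would have had a film and which benefits reach participants ask only for clearer text. No change to the plan follows; tidying the wording is housekeeping.

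This rests on three assumptions. The doses of 24 and of 85 or 87 are the ones the authors meant to compare. The panoramic film belongs to a work-up done when radiation is possible; if it does not, affected participants bear 24 microSv more than the net figure, in unknown number. And the consent form, which I have not seen, does not rely on the 40.

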5.4 Method for Assigning Subjects to Treatment Groups

This study will not be randomized. All patients will received a helical CT, PET/CT and CBCT

5.6 Subject Compliance Monitoring

In this study, compliance is minimized in that once the imaging is completed and the surgical treatment carried out, the patient will have little commitment to the study.

5.7 Prior and Concomitant Therapy

In this section, describe:

- What prior and/or concomitant medical therapy will be collected (if applicable):
 - None
- Which concomitant medicines/therapies (including rescue therapies) are permitted during the study:
 - Any that are prescribed by the medical oncologist, given that the imaging is unrelated
- Which concomitant medicines/therapies are not permitted during the study (if applicable):
 - Radiation to the mandible or maxilla

6.0 STUDY PROCEDURES

6.1 Study Visit Schedule

Screening: Once patients are referred to the OMFS or JHNS departments with oral SCC, they will be evaluated to see if they meet the inclusion criteria and do not satisfy the exclusion criteria. Once they are deemed a candidate for the study by one of the involved doctors, they will have an appointment setup for a CBCT

Visit 1: CBCT in OMFS Office

Visit 2: Surgical planning in JHNS office, blinded to the result of the CBCT

Definitive Surgical Treatment

Follow-up: The patient will follow up in the JHNS department for necessary adjuvant therapies and post-surgical care when surgical treatment is carried out.

Please see the appendix for an outline of the study and also a card that will be posted in both JHNS and OMFS office to be used when evaluating patients for inclusion

Procedures, situations, or materials that may be hazardous to personnel and the relevant precautions, should also be outlined here.

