1.1 Specific Aims and Hypothesis

There are newer imaging modalities that have not been studied sufficiently to determine whether intraoral SCC has or has not infiltrated a segment of the mandible or maxilla, necessitating partial or complete resection of the jaw. One such modality is cone beam CT (CBCT), which delivers approximately 1/6 the amount of radiation and is about 1/10 the cost of a multi-slice, helical CT¹. A previously published imaging protocol by Van Cann et al² used MRI, CT and bone SPECT to image the mandible. In contrast to the prior algorithm, this study aims to test newer modalities such as the CBCT, PET/CT and helical CT against more traditional imaging techniques, to attempt to detect neoplastic infiltration of the mandible and maxilla. We hypothesize that CBCT or a combination of the aforementioned modalities can be used in order to more accurately predict invasion of the maxilla or mandible by intraoral SCC.

The accurate prediction of the presence or absence of malignant invasion of the jaws greatly influences the surgical treatment plan. This is important for several reasons. First, it may change the staging of the disease, necessitating a more or less involved resection and reconstruction. Second, this knowledge will greatly benefit the surgeon, since the reconstruction of an extensive surgical defect will be more complex and require greater planning. In addition, occult infiltration of the jaws may be a source of locoregional regrowth and recurrence that may be detectable by such imaging, leading to a wider, more appropriate and oncologically sound resection. Third, if absence of mandibular or maxillary invasion can be proven statistically, it will permit “sparing” of complete or partial resection. Thus, the mandible and maxilla, which are critical to facial form and function, will be preserved in some form and improve the overall quality of life of the cancer patient.

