3.0 STUDY DESIGN

3.1 General Design

Prospective, non-randomized, double blinded study

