3.3 Secondary Study Endpoints

The secondary endpoint would be to more accurately plan the resection of mandibular or maxillary bone if invasion is predicted. If invasion is not predicted based upon the imaging modalities, then the secondary endpoint would be to spare resection of uninvolved bone

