13.0 PUBLICATION PLAN

Once imaging and histologic data have been collected from the target sample size, the information will be compiled for publication. This information will not be published in any manner prior to official publication

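### Surgical planning is blind to CBCT only and only resected bone is verified, so helical CT and PET/CT sensitivity may be inflated relative to CBCT; the effect on specificity and accuracy depends on how unverified patients are handled

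*Combined protocol and SAP*

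**What the plan says.** The only working description of blinding at surgical planning is in 6.1: "Visit 2: Surgical planning in JHNS office, blinded to the result of the CBCT". Section 3.1 calls the study "Prospective, non-randomized, double blinded study" without saying who is blinded to what. Section 8.3 would release the information to the oncologic surgeon once any modality or combination proves accurate, with no timing or threshold.

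Every patient has all three scans (5.4: "All patients will received a helical CT, PET/CT and CBCT"). The comparators are ordinary care (1.3; 5.2: "Currently, helical CT and PET/CT are routinely used"). Section 1.1 ties imaging to surgery: "The accurate prediction of the presence or absence of malignant invasion of the jaws greatly influences the surgical treatment plan". Section 3.3 adds: "If invasion is not predicted based upon the imaging modalities, then the secondary endpoint would be to spare resection of uninvolved bone".

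The reference standard is histology of the specimens (7.2), which the Appendices specify as resected specimens. Section 7.2 defines a false positive as positive imaging with no histologic evidence, without separating bone examined and found negative from bone never examined. Section 7.3 analyses everyone enrolled and consented. No reference is given for bone left in place: the Study Summary lists follow-up as not applicable, 6.1 describes follow-up for care only, and 13.0 says "Once imaging and histologic data have been collected from the target sample size, the information will be compiled for publication".

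**The concern.** In a paired accuracy study, each test should have the same influence on who receives the reference standard, preferably none. Here two of the three tests may influence it and the third does not. The patient who would best support the hypothesis in 1.1 is CBCT-positive, negative on CT and PET/CT, and truly invaded. If planning follows the scans the surgeon can see, that patient is among the least likely to have bone resected and examined.

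The primary objective (2.1) is to find the most accurate modality or combination, and patients with discordant scans decide that ranking. If their verification depends on the comparators, more patients would not remove the bias. The exclusion of obvious clinical invasion of the mandible (4.2) leaves imaging with more weight in the bone decision.

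**Working it through.** **Figures in the plan.** The documents give no expected accuracy, prevalence or verification rate, so there is no stated figure to reproduce. The Study Summary gives 20 subjects, the appendix schema shows N=10, and 7.1 bases the number on case volume. All accuracies, the prevalence and r below are assumptions.

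**1. Sensitivity, CT alone steering resection.** True sensitivity is 70% for CT and 90% for CBCT, and errors are independent given true status. All CT-positive patients have bone resected, as does a share r of CT-negative patients. Per 100 invaded patients, 70 + 30r are verified:

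apparent CT sensitivity = 70/(70 + 30r)

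| r | CT | CBCT |
|---|---|---|
| 1 | 70.0% | 90% |
| 0.5 | 70/85 = 82.4% | 90% |
| 0.2 | 70/76 = 92.1% | 90% |

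The two are equal when 70 + 30r = 70/0.90 = 77.8, so r = 0.26. With true CT sensitivity of 80%, the crossing is at 0.80 × 0.10/(0.90 × 0.20) = 0.44.

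**2. Dependent errors.** With true values of 90% and 80%, and positive dependence at half its maximum, r = 0.5 gives CBCT 92.2% and CT 88.9% (no reversal). At r = 0.25 the figures are 93.5% and 94.1% (reversal). The direction is the same and the bias is smaller.

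**3. Either CT or PET/CT triggers resection (independent errors).**
- CT 70%, PET/CT 70%: 1 − 0.3 × 0.3 = 0.91 of invaded patients are verified even at r = 0, so CT reads 0.70/0.91 = 77%. This does not overtake CBCT at 90%.
- CBCT 85%, CT 80%, PET/CT 60%: at r = 0, CT reads 0.80/0.92 = 87% and does overtake.
- CT 70%, PET/CT 60%: the combination (either positive) has true sensitivity 1 − 0.3 × 0.4 = 88%. It reads 0.88/(0.88 + 0.12 × 0.5) = 93.6% at r = 0.5 and 100% at r = 0, above CBCT at 90%. This matters because 2.1 also asks about combinations.

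**4. Specificity and accuracy.** Take step 1 at r = 0.2, with specificity 90% for both tests and prevalence 30%. Per 1,000 patients, 300 are invaded (CT: 210 positive, 90 negative) and 700 are not (CT: 70 positive, 630 negative). Verified: 210 + 18 = 228 invaded and 70 + 126 = 196 not invaded, 424 in all. That leaves 72 invaded patients unverified.

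- *Unverified dropped.* CT specificity is 126/196 = 64% and CT accuracy (210 + 126)/424 = 79%. CBCT stays at 90% on both.
- *Unverified counted as histology-negative.* The negatives number 700 + 72 = 772. CT specificity is (630 + 72)/772 = 90.9% and accuracy (210 + 702)/1,000 = 91.2%. CBCT false positives are 70 + 0.9 × 72 = 134.8, so its specificity is 637.2/772 = 82.5% and its accuracy (205.2 + 637.2)/1,000 = 84.2%.

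| Accuracy | CT | CBCT |
|---|---|---|
| True | 84% | 90% |
| Unverified dropped | 79% | 90% |
| Counted as negative | 91% | 84% |

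**5. At 20 patients.** This is a simulation with prevalence 30%, sensitivities 90% and 70%, and CT alone steering. The chance that CT ranks above CBCT on sensitivity is 9% with full verification, 25% at r = 0.25 and 35% at r = 0. The chance that CBCT ranks above CT is 68%, 24% and 0%.

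**The case against.** **The mechanism is inferred.** No section says outright that the surgeon chooses the bone from CT or PET/CT. The double-blind label in 3.1 and the wording of 8.3, which refers to any imaging study or combination, could mean that more than CBCT is withheld. Bone may also be resected on clinical, MRI or intraoperative grounds. This stands: invasion missed by the comparators may go unverified, not must. The inference is still well supported, because 6.1 names CBCT alone, 1.3 and 5.2 make the other scans routine care, and 1.1 and 3.3 link predicted invasion to what is removed.

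**A reader might infer that the whole comparison is biased against CBCT and the primary objective answered in the wrong direction.** The documents do not support that. It holds for sensitivity, and for the literal reading of 7.2 with 7.3. If unverified patients are dropped, specificity and accuracy tilt towards CBCT (step 4).

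**A reader might take r below 0.26 as a general threshold for reversal.** It belongs to a single steering test with independent errors. Steps 2 and 3 show reversal is harder for a single modality when either scan can trigger resection, and the bias smaller when errors are dependent.

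**A reader might also take 1.1 as saying that missed invasion will appear later as recurrence.** It says only that "occult infiltration of the jaws may be a source of locoregional regrowth and recurrence that may be detectable by such imaging". Follow-up is therefore an imperfect reference.

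**The ranking is fragile anyway.** At 30% prevalence, 20 patients include about 6 with invasion, and even full verification ranks CBCT above CT only 68% of the time. This is true, but it is sampling error; dependence of verification on the comparators adds a systematic error.

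**Conclusion.** The point holds in this form: verification may depend on helical CT and PET/CT but not on CBCT, which inflates the comparators' sensitivity relative to CBCT. The ranking on sensitivity can reverse when few comparator-negative patients have bone resected. In the single-steering-test illustration, a true 20-point CBCT advantage falls to about 8 points at r = 0.5 (90 − 82.4) and reverses at r = 0.2.

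For specificity and accuracy, the direction depends on handling. Under the literal wording, a CBCT-positive, CT-negative patient with invaded but unresected bone is a CBCT false positive and a CT true negative. In step 4 that turns a true 6-point CBCT lead in accuracy into a 7-point deficit, while dropping unverified patients widens the lead to about 11 points.

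These sizes rest on assumed accuracies, prevalence and r. The direction for sensitivity rests on the inference that the comparators influence resection and on the CBCT blind holding throughout. The plan should be changed, because what the surgeon had seen at planning is hard to reconstruct afterwards.

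**What to change.** 1. At Visit 2, record on the CRF the planned bone resection (none, marginal, segmental, maxillectomy) and which scan results the surgeon had seen.
2. Amend 7.2 and 7.3 so that patients without bone histology are classed as not histologically verified, not as histology-negative. Report delayed verification separately: jaw recurrence or its absence, from existing JHNS follow-up records at one fixed time point, with adjuvant radiation noted.
3. Report the modality comparison by agreement pattern (for example CBCT-positive/CT-negative) with the verified share in each, plus a best-case and worst-case analysis for unverified patients. Keep any verification-bias weighting exploratory. CT, PET/CT and clinical-examination results form up to 2 × 2 × 2 = 8 cells for 20 patients, so empty cells are likely, and the weighting relies on a CBCT blind that 8.3 may lift.
4. Align the data cut in 13.0 and the two-year duration in the Study Summary with that time point.
5. Reconcile 6.1 and 8.3 with the double-blind label. Reconcile 5.7, which lists radiation to the mandible or maxilla as not permitted during the study, with the adjuvant therapies in 6.1.

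The cost is a short CRF entry and a chart review of visits that already occur, with no added procedure or patients. The downsides are a later data cut, shorter follow-up for late enrolees, and imperfect delayed verification, because adjuvant treatment can mask residual disease.
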